 - Some patients on IrCs experience mild clumsiness, tremor, nausea or abdominal griping during the three days of Cs treatment. Reassurance and general symptomatic treatments are normally sufficient; but if severely affected, reduce the Cs dose to 2 mg/kg t.d.s. for the remainder of the cycle and for all subsequent cycles.

- Some patients find the smell or taste of Cs foul. We recommend:
 - try switching from gelatin capsules to liquid or vice versa
 - “pop” the capsule blister-packs out-doors to avoid the smell
 - liquid may be mixed with orange juice to disguise the taste
- If a patient on IrCs is unable to tolerate Cs even with the above measures, they should cross over to standard Ir. However please see note in 6.5 regarding irinotecan dosing.

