6.5 Cross-over

- Crossover involving ciclosporin:
 - Cross-over from **IrCs** to **Ir** should be avoided if possible, however if a patient cannot tolerate Cs this may be necessary. Please inform the CTRU.
 - the half-life of Cs is around 6 hours in most patients but may be as long as 20 hours. Therefore at least 1 week wash-out time must be allowed after the patient took their last Cs dose, before they receive standard-dose Ir.
 - Cross-over from **Ir** or **IrPan** to **IrCs** is not permitted
- Crossover involving Panitumumab:
 - Cross-over from **IrPan** to **Ir** should be avoided if possible, however if a patient cannot tolerate Pan this may be necessary. Please inform the CTRU.
 - Cross-over from **Ir** or **IrCs** to **IrPan** is not permitted.

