6.8 Pharmacokinetics Sub-study (see Appendix 4)

- In 20 consenting patients recruited to the IrCs arm in 2-4 centres with pharmacokinetics (PK) expertise, the plasma AUC of Ir and its metabolites will be compared during Ir and IrCs treatments during two consecutive cycles as follows:
 - For patients allocated **IrCs**, and participating in the PK Sub-study, two consecutive cycles during the first 4 cycles of therapy (i.e. cycles 1 & 2, cycles 2 & 3 or cycles 3 & 4) will be nominated as PK Sub-study cycles
 - For these two cycles the patient will receive, in random order, one cycle of IrCs and one cycle of standard Ir
 - PK blood sampling will be performed during the nominated cycles, as per Appendix 4

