11. STATISTICAL CONSIDERATIONS

11.1 Sample Size

Ir vs IrCs comparison

A non-inferiority design is proposed, based upon the proportion of patients progression-free at 12 weeks from randomisation. In a previous study in a similar patient population receiving irinotecan, median PFS was 4.2 months, with 63.3% of patients progression-free at 12 weeks.³⁸ There are no previous best supportive care (BSC) trials that have included regular CT scan assessments, however in a trial comparing irinotecan with BSC, at the time point that 63% of Ir

patients were alive, less than 40% of BSC patients were alive⁴⁰. On this basis we have estimated that a similar proportion – 40% - of patients on BSC would be expected to be progression-free at 12 weeks applying standard WHO or RECIST criteria. On this basis irinotecan contributes at least 23% to the proportion of patients progression-free at 12 weeks. On the basis of clinician consensus IrCs will be defined as no worse than Ir if median PFS is at least 3 months with IrCs, equivalent to at least 52.7% of patients in the IrCs arm progression-free at 12 weeks. This corresponds to a reduction of no more than 10.6% in the proportion of patients progression-free at 12 weeks which is our non-inferiority margin; retaining more than half the effect that irinotecan has over BSC. The sample size calculation for the Ir vs. IrCs comparison remains the same since there is no data to suggest that *K-RAS* status is a predictive factor for Irinotecan or Ciclosporin.

We will conduct a one-sided test for non-inferiority.³⁹ With 80% power and a significance level of 2.5%, 680 patients are required to test for this degree of non-inferiority using a one-sided chi-squared test without continuity correction. To account for a 10% drop-out or 5% cross-over, 750 patients (375 per arm) would need to be randomised in total. This sample size also gives over 90% power for claiming non-inferiority of PFS using a one-sided modified log-rank test with significance level 2.5% (at least 273 PFS events are required to assess non-inferiority with 80% power), and allows detection of a clinically relevant relative reduction of 50% (from 20% with Ir to 10% with IrCs) in the proportion of patients experiencing grade 3+ diarrhoea within 12 weeks of randomisation, with over 90% power and at a 5% (two-sided) significance level, using a two-sided chi-squared test without continuity correction.

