12. STATISTICAL ANALYSIS

Statistical analysis is the responsibility of the CTRU Statistician. A final statistical analysis plan corresponding to Protocol Version 1.0 has been written in accordance with current CTRU standard operating procedures and has been finalised and agreed by the following people: the trial statistician and supervising statistician, the project manager and the Chief Investigator. Changes to this finalised analysis plan, and reasons for changes, will be documented. The above people will remain blinded to the data and will not have access to the complete CRFs.

All analyses will be conducted on the intention-to-treat (ITT) population (as defined in the statistical analysis plan), where patients will be included according to the treatment they were randomised to, and the per-protocol population (if necessary), where patients will be included according to the treatment they received. Patients defined as major protocol violators will be excluded from the per-protocol analysis. Major protocol violators were defined prior to the start of recruitment and any subsequent changes, and reasons for changes, will be documented. For the superiority endpoints the ITT analysis will be given primacy, however for the non-inferiority endpoints equal weighting will be given to both the ITT analysis and the per-protocol analysis, as the ITT is likely to be the least conservative approach when testing for non-inferiority. The safety population will consist of all patients who receive at least one dose of study treatment, and will be considered as necessary.

Overall survival is defined as the time from date of randomisation to date of death from any cause; patients with missing follow-up data, or who are still alive at the time of analysis, will be censored at the last date they were known to be alive. Progression-free survival is defined as the time between date of randomisation and date of disease progression or death from any cause. Patients with missing follow-up data, or who are alive and progression-free at the time of analysis, will be censored at the date they were last known to be alive and progression-free.

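### The per-protocol set is grouped by treatment received and worded as optional, although it carries equal weight with ITT for the non-inferiority of IrCs

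*Protocol*

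**What the plan says.** Protocol section 12 names two populations. ITT follows randomisation. The other is "the per-protocol population (if necessary), where patients will be included according to the treatment they received". Two further rules apply to it: "Patients defined as major protocol violators will be excluded from the per-protocol analysis", under a definition fixed before recruitment that this document does not reproduce; and "for the non-inferiority endpoints equal weighting will be given to both the ITT analysis and the per-protocol analysis", on the ground that ITT tends to be the less conservative analysis for non-inferiority.

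The clinical sections determine who can have received something other than the allocated regimen:

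- Section 6.4: "If a patient on IrCs is unable to tolerate Cs even with the above measures, they should cross over to standard Ir".
- Section 6.5 says cross-over from IrCs to Ir should be avoided if possible, "however if a patient cannot tolerate Cs this may be necessary". Cross-over from Ir or IrPan to IrCs "is not permitted".
- Section 6.8, for the 20 PK sub-study patients, all drawn from the IrCs arm: "For these two cycles the patient will receive, in random order, one cycle of IrCs and one cycle of standard Ir".

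Section 11.1 sets the control rate ("with 63.3% of patients progression-free at 12 weeks"), a margin of 10.6 percentage points (IrCs at least 52.7%), and 680 patients, raised to 750 for 10% drop-out or 5% cross-over.

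**The concern.** A per-protocol analysis normally keeps patients in the arm to which they were randomised and drops those who departed materially from the protocol. A rule that assigns patients by what they took regroups them on a post-randomisation event. Here that event can occur in only one direction, from IrCs to Ir, and it is triggered by intolerance of the experimental component.

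A patient who switches has received both regimens, and so has every PK sub-study patient. The protocol does not say which regimen then counts as the one received. A switch for ciclosporin intolerance follows section 6.4, so nothing shown makes it a major violation.

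The per-protocol analysis is there to guard against ITT being too lenient. If it can itself be shifted toward non-inferiority, agreement between the two analyses reassures less than it appears to. Separately, an analysis with equal weight cannot also be one whose conduct is decided later.

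**Working it through.** **Plan's own figure.** With 63.3% and 52.7% (mean 58%), one-sided 2.5%, 80% power, pooled variance and no continuity correction:

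n per arm = [1.96·√(2·0.58·0.42) + 0.8416·√(0.633·0.367 + 0.527·0.473)]² / 0.106² = 339.2, so 340 per arm and 680 in total, as stated. Inflation gives 680/0.9 = 756, 680×1.1 = 748 or 680/0.95² = 754; the stated 750 is close to all three.

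**Effect of the grouping rule.** Inputs: 375 per arm; truth as randomised exactly on the margin (63.3% Ir, 52.7% IrCs); 19 IrCs patients (5% of 375) counted as Ir. The movers' 12-week progression-free rate r is not in the protocol, so a range is used. Simplifications: all 5% switch from IrCs before the 12-week assessment, and the test is an unadjusted Wald limit for the difference, not the covariate-adjusted odds ratio.

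- IrCs as grouped = (375×0.527 − 19r)/356
- Ir as grouped = (375×0.633 + 19r)/394
- d = Ir − IrCs
- one-sided error = Φ((0.106 − d)/SE − 1.96), with n = 356 and 394

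Example, r = 30%: IrCs = (197.625 − 5.7)/356 = 53.9%; Ir = (237.375 + 5.7)/394 = 61.7%; d = 7.8 points; SE = 0.0360; error = Φ(0.78 − 1.96) = about 12%.

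The last column leaves the same 19 patients out instead of moving them (356 against 375).

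| Movers' rate r (assumed) | d if moved (points) | Error if moved | Error if excluded |
|---|---|---|---|
| 20% | 6.8 | about 18% | 7.0% |
| 30% | 7.8 | 12% | 5.2% |
| 40% | 8.8 | 7% | 3.8% |
| 52.7% | 10.1 | 3.5% | 2.5% |
| 63.3% | 11.2 | 1.7% | 1.7% |
| 80% | 12.9 | 0.5% | 0.9% |

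As randomised, the error is 2.5%.

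**Break-even.** d is linear in r: d = 237.375/394 − 197.625/356 + r(19/394 + 19/356) = 0.0474 + 0.1016r. Setting d = 0.106 gives r = about 58%. Below that the regrouping favours IrCs; above it, it works against IrCs.

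**Joint error.** If a claim needs both analyses to meet the margin, the probability of a false claim cannot exceed that of ITT, 2.5% in this scenario. If either analysis were enough, it could not be less than the larger of the two. The protocol does not say which of these equal weight means.

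**Optionality.** The bracketed qualifier and the equal-weight sentence stand in one paragraph. The first leaves the analysis to later judgement; the second presupposes that it is done.

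**The case against.** A reader might infer that the plan moves ciclosporin-intolerant patients into the control arm. The documents do not say so. These patients received both regimens, no rule says which one counts, and the list of major violators, or an analysis plan not shown, may exclude or classify them. What stands is that the wording allows the move.

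A reader might also infer that the per-protocol analysis is biased toward non-inferiority. That is not shown. Sections 1 and 6.4 describe ciclosporin intolerance as nausea, cramps, tremor or distaste, not as tumour progression. A patient who switches must still be fit for irinotecan after at least a one-week wash-out, which may select patients who have not progressed. At movers' rates of 63.3% and above, the regrouping is conservative.

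The qualifier applies to a sentence about all analyses, superiority endpoints included, so the equal-weight sentence can be read as making the analysis necessary for non-inferiority. That reading is reasonable, but the text should state it.

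Two points limit the size. The error figures belong to the per-protocol set alone and are not the trial's error rate. Part of the excess also remains if cross-overs are excluded, because exclusion after randomisation is selective too. In addition, section 11.1 gives no direction or timing for its 5%, and switches after 12 weeks cannot affect the primary endpoint.

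The PK patients are the weaker part: section 5.2.1 gives them IrCs in all other cycles, so their main regimen is clear even though the rule is silent. The DMEC's review of cross-over in section 12.1 concerns sample size and does not settle how these patients are analysed.

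**Conclusion.** The point holds as a defect of wording that can change a result. The protocol itself fixes an as-treated grouping under the per-protocol name, and it words as optional an analysis that it also weights equally with ITT. Both need correcting before the Ir versus IrCs comparison is analysed, because choosing the rule once the cross-overs are known would weaken the primary claim.

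The size is conditional. At 5% regrouped and the truth on the margin, the per-protocol error alone runs from about 18% (movers at 20%) to 0.5% (movers at 80%), against a nominal 2.5%. It is 3.5% if movers do exactly as well as their own arm and returns to nominal at about 58%. These figures rest on an assumed movers' rate and on cross-overs being counted as Ir, which the wording permits but does not state. ITT and the sample size of 680/750 are unaffected.

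**What to change.** For the non-inferiority endpoints in section 12:

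1. Delete the bracketed qualifier, so that the per-protocol analysis is always done.
2. Replace grouping by treatment received with grouping by randomised arm. Patients may be excluded under pre-listed criteria but are never moved between arms.
3. State in advance how IrCs-to-Ir cross-overs before the 12-week assessment are handled. If they are excluded, acknowledge that exclusion is also selective.
4. Keep PK sub-study patients in IrCs, with a sensitivity run without them.
5. State that equal weight means both ITT and per-protocol must meet the margin for a claim.
6. Label any as-treated analysis as a sensitivity analysis only.

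The cost is a documented wording change in the protocol and analysis plan, and a slightly lower chance of a positive claim because both sets must pass. No clinical rule and no sample size changes.

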2. AIMS AND OBJECTIVES

PICCOLO has two separate clinical objectives. These are:

Objective 1 (irinotecan modulation with ciclosporin): to establish whether the toxicity of irinotecan therapy is reduced, without loss of efficacy, by modulation with ciclosporin

Objective 2 (addition of panitumumab): to establish whether, in patients with *K-RAS* wild-type tumours, the efficacy of irinotecan therapy is improved by the addition of panitumumab

To address these objectives, the trial poses specific questions using primary and secondary endpoints, fully described in section 10. The general approach is:

Objective 1 (comparison: Ir versus IrCs).

- A sensitive primary outcome measure – proportion of patients alive without evidence of disease progression 12 weeks after randomisation – is used to establish non-inferior anti-cancer efficacy for the **IrCs** combination
- Provided this non-inferiority condition is satisfied, secondary outcome measures will be used to determine whether **IrCs** has improved tolerability (reduced diarrhoea; reduced overall toxicity; improved patient acceptability and/or improved quality of life). In addition, overall survival will be used as a secondary outcome measure to confirm non-inferiority.

Objective 2 (comparison: Ir versus IrPan).

- A robust primary outcome measure – overall survival – is used to establish whether, in patients with *K-RAS* wild-type tumours not previously treated with anti-EGFr therapy, **IrPan** has superior efficacy to Ir.
- Secondary outcome measures will be used to compare the toxicity, patient acceptability and quality of life associated with the two regimens in patients not previously treated with anti-EGFr therapy. Secondary anti-cancer efficacy measures of disease response and progression will also be applied to assess superiority of IrPan in these patients.
- A small proportion of patients will have received a prior anti-EGFR targeted therapy. They will be considered in a separate exploratory comparison of efficacy using a sensitive outcome measure (proportion of patients progression-free at 12 weeks) to address the question whether panitumumab enhances irinotecan sensitivity in this context and to also assess toxicity. This exploratory analysis will consider only those patients with wild-type *K-RAS* status who have previously received an anti-EGFR targeted therapy.

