5.3 Baseline and reassessment CT scan

The baseline CT scan **must be within 4 weeks prior to the start of trial treatment**, so a repeat CT should be organised if required, remembering that randomisation cannot take place until *K-RAS* mutation status has been determined. Limited funding is available to contribute towards the cost of repeat baseline CT scans that are required only to meet the timelines set out in this protocol. Funding is available up to a limit of £150 per-patient at the time of writing this protocol. Please contact the CTRU for current funding availability.

Radiological reassessment is made **12 weeks after randomisation** ("12 week scan"), then at 12-weekly intervals, or sooner if clinically indicated, until disease progression ("follow-up scans"). It is recommended that the 12 week scan is pre-booked, at the time of starting treatment, **as near as possible to exactly 12 weeks after the date of randomisation** (with up to a further two weeks allowed in order to take account of practical issues).

If there is clinical evidence of disease progression at a time other than when radiological reassessment is due a CT scan should be carried out to confirm progression. A CT scan should always be carried out to confirm disease progression, unless there is a compelling reason not to.

Please note that copies of the baseline and the 12 week scan are required for external review. The preferred format is CD Rom, but hard-copy films are also acceptable. These should be forwarded to the PICCOLO team, CTRU, University of Leeds, [name] with their reports, as soon as possible after the 12 week scan has been performed. The scans and reports should be anonymised and labelled with the patient's trial number only. CTRU will provide pre-paid Special Delivery envelopes in which to send the CT scans for central review.

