7.7 Progress and Follow-up Assessment

Follow-up data will be collected at 24 weeks post-randomisation and 12-weekly thereafter for all patients until 48 weeks post-randomisation, or until 6 weeks after the last PICCOLO treatment, whichever is later. The information required at these time-points includes late toxicity (adverse events occurring up to six weeks after the last dose of irinotecan), subsequent therapy and death.

The following investigations and assessments will be carried out:

- CT scan and response by RECIST criteria (if progression has not previously occurred).
- Toxicity assessed by NCI-CTC[V3] grades (up to 6 weeks after last study treatment dose)

In addition the following data will be collected:

- Patient status
- Summary of trial treatment since last assessment
- Details of any non-trial anti-cancer treatment received since last assessment
- Clinical evidence of disease progression or not
- Treatment plan
- Quality of Life questionnaires at 24 weeks post-randomisation (for details refer to section 7.9)

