10. ENDPOINTS

10.1 Primary Endpoint

Ir vs IrCs comparison

- Proportion of patients progression-free 12 weeks after randomisation.

Ir vs IrPan comparison (patients with wild-type K-RAS status not previously receiving an anti-EGFR targeted therapy)

- Overall survival (OS) from randomisation

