Analysis of 12-week assessments will include all patients assessed between 10 and 14 weeks from randomisation. A sensitivity analysis will be conducted to allow for patients assessed outside of this 2 week time frame. Analysis of response will be performed using the centrally reviewed outcome. If the centrally reviewed outcome is missing, the primary analysis will class the patient as being progression-free at 12 weeks (if alive), and a sensitivity analysis will be conducted using the outcome of the local assessment. If this is also missing, the patient will be classed as having progressed at 12 weeks in the sensitivity analysis.

A two-sided 5% significance level will be used for all superiority endpoints, and a one-sided 2.5% significance level will be used for all non-inferiority endpoints.

Safety data (adverse events and serious adverse events as detailed in Section 8) will be presented for all patients by treatment group and comparison, and by relationship to study drug, or underlying colorectal cancer.

Ir vs IrCs comparison

All patients randomised to receive either Ir or IrCs via protocol Version 1.0 or to the Ir vs. IrCs comparison under protocol Version 2.0 (i.e. mutant/unknown *K-RAS* status), regardless of previous anti-EGFR targeted therapy use, will be included in this comparison.

Primary Endpoint

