Analysis will be based on the lower limit of the 95% confidence interval (CI) (one-sided type I error rate of 2.5%) of the difference in proportion of patients progression free at 12 weeks from randomisation between each treatment group. Logistic regression will also be used to adjust for the minimisation factors, previous anti-EGFR targeted therapy use and any other covariates identified to influence patients' prognosis. Treatment and covariate estimates with corresponding 95% CIs will be given. To account for any deaths from causes other than colorectal cancer which may occur within 12 weeks of randomisation, for whom no evidence of disease progression was found, sensitivity analyses will be conducted classifying these patients as progression-free (these patients will be classed as having progressive disease at 12 weeks in the main analysis). Sensitivity analysis will also be conducted to account for patients with missing data regarding progression at 12 weeks, using the local assessment or classifying these patients as with progressive disease, as appropriate. The primary analysis will be based on the lower limit of the confidence interval of the odds ratio for the proportion of patients progression free at 12 weeks, obtained using logistic regression which adjusts for the minimisation factors.

Secondary Endpoints

The difference in proportion of patients who are free from treatment failure, defined as clinical or radiological progression, death due to colorectal cancer or toxicity, or termination of treatment irrevocably, at 12 weeks from randomisation between treatment groups will be compared using a two-sided chi-squared test. Logistic regression will also be used to adjust for the minimisation factors, previous anti-EGFR targeted therapy use and any other covariates identified to influence patients' prognosis. Treatment and covariate estimates with corresponding 95% CIs will be given. Sensitivity analyses will be conducted to allow for any deaths from causes other than colorectal cancer within 12 weeks of randomisation. Sensitivity analysis will also be conducted to account for patients with missing data regarding treatment failure at 12 weeks, classifying these patients as with treatment failure.

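### The week 10 to 14 inclusion rule leaves a living patient with earlier documented progression either out of the primary non-inferiority analysis or liable to be counted as progression-free

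*Protocol*

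**What the plan says.** The primary endpoint for Ir vs IrCs (Protocol 10.1) is "Proportion of patients progression-free 12 weeks after randomisation". Section 2 spells it out as the "proportion of patients alive without evidence of disease progression 12 weeks after randomisation".

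Section 12 sets the rule for who is analysed: "Analysis of 12-week assessments will include all patients assessed between 10 and 14 weeks from randomisation". It continues: "A sensitivity analysis will be conducted to allow for patients assessed outside of this 2 week time frame". This stands in the general part of section 12, so it governs both the Ir vs IrCs primary endpoint and the 12-week secondary endpoint of Ir vs IrPan.

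Four other statements bear on the same patients:
- Section 12 opens with "All analyses will be conducted on the intention-to-treat (ITT) population", as defined in the SAP, and its Ir vs IrCs part takes in everyone randomised to either arm under either protocol version.
- Section 12 scores a living patient with no centrally reviewed outcome as progression-free in the primary analysis. The local read is used only in a sensitivity analysis.
- For deaths within 12 weeks from causes other than colorectal cancer with no progression found, section 12 says "these patients will be classed as having progressive disease at 12 weeks in the main analysis".
- Section 5.3 says that with clinical evidence of progression "at a time other than when radiological reassessment is due a CT scan should be carried out to confirm progression". It schedules scans until progression and names only the baseline and 12-week scans as required for external review.

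**The concern.** Membership of the main analysis depends on an event after randomisation, being assessed in a four-week window, and that event is linked to the outcome. A patient with progression confirmed at week 6 is a known failure of the endpoint, yet no sentence says how that patient enters the main analysis.

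There are two possible routes. If the window sentence is applied as written and the patient has no assessment at weeks 10 to 14, a failure leaves the denominator. If the intention-to-treat text overrides the window, the patient stays in. But there may then be no central 12-week read, and the default for that case is progression-free. The first route removes a failure and the second turns a failure into a success. When the share affected is similar in the two arms, the arm with more early failures gains more. At the plan's own rates, the Ir minus IrCs difference then shrinks, and a non-inferiority claim becomes easier when IrCs is truly worse.

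**Working it through.** **Inputs from Protocol 11.1:** 63.3% (Ir) and 52.7% (IrCs at the limit) progression-free at 12 weeks; margin 10.6 points; one-sided 2.5%; 80% power; 680 patients, raised to 750 (375 per arm).

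**Assumptions not in the documents:** exponential progression-free survival through those 12-week rates; the same share of events affected in each arm; a range for that share. The calculation is on the risk-difference scale, on which the margin is stated.

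**1. The plan's figure.** With p̄ = (0.633 + 0.527)/2 = 0.58,

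n per arm = [1.96·√(2·0.58·0.42) + 0.8416·√(0.633·0.367 + 0.527·0.473)]² / 0.106² = 339.2, rounded up to 340, or 680 in total. The plan's number is reproduced.

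**2. Events before week 10.** S(10) = S(12)^(10/12).
- Ir: 0.633^(10/12) = 0.683, so 375 × 0.317 ≈ 119 patients.
- IrCs: 0.527^(10/12) = 0.586, so 375 × 0.414 ≈ 155 patients.

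**3. Route one: a share f of these is dropped.** In each arm p′ = S(12)/[1 − f(1 − S(10))] and n′ = 375·[1 − f(1 − S(10))]. With d the new difference and an unpooled standard error,

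P(false non-inferiority) = Φ[(0.106 − d)/SE − 1.96].

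| f | Ir | IrCs | d (points) | SE (points) | False non-inferiority |
|---|---|---|---|---|---|
| 0 | 63.3% | 52.7% | 10.6 | 3.58 | 2.5% |
| 10% | 65.4% | 55.0% | 10.4 | 3.62 | 2.8% |
| 25% | 68.7% | 58.8% | 10.0 | 3.66 | 3.7% |
| 50% | 75.2% | 66.4% | 8.8 | 3.66 | 7.2% |
| 75% | 83.0% | 76.4% | 6.6 | 3.45 | 20.9% |
| 100% | 92.7% | 89.9% | 2.8 | 2.61 | 85% |

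**4. Route two: a share f of patients with an event by week 12 is scored progression-free.** Now p′ = S(12) + f·[1 − S(12)], so d = 10.6·(1 − f), with 375 per arm.

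| f | d (points) | False non-inferiority |
|---|---|---|
| 5% | 10.1 | 3.5% |
| 10% | 9.5 | 4.9% |
| 20% | 8.5 | 9.0% |
| 30% | 7.4 | 15.8% |

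The default applies only to living patients, so f here can come only from living progressors.

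**5. Late scans, excluded unrelated to arm and outcome.** The rates do not move, so the error at the margin stays at 2.5%. Power at 63.3% in both arms, with 375 per arm, falls from 85.3% to 83.5%, 81.5% or 76.8% if 5%, 10% or 20% are excluded.

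**The case against.** The best defence is that the window sentence only identifies which scans count as the 12-week assessment and does not set the denominator. The intention-to-treat statement and the inclusion of all randomised patients support this. So does the rule on non-cancer deaths: a dead patient cannot be assessed at week 10 yet is counted in the main analysis. The SAP, not available for this review, defines the intention-to-treat population and may settle the matter.

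Much of this stands, and it limits the point in four ways.
- **Deaths.** A reader might infer that anyone who dies before week 10 falls out. The documents do not support that. Non-cancer deaths without progression are failures by express rule, cancer deaths fail the endpoint as worded in section 2, and the progression-free default is limited to living patients.
- **The 12-week visit.** Section 7.6 schedules a 12-week CT and a record of clinical progression without exempting patients who have already progressed, so some would be assessed in the window. The words "CT scan and response by RECIST criteria (if progression has not previously occurred" come from section 7.7, which covers week 24 onward. Only the scanning-until-progression wording in 5.3 suggests that an early progressor may not be rescanned.
- **Timing.** Section 10.4 relies on a single mandatory assessment point, and earlier CT follows only clinical suspicion. Much progression would first be documented at the 12-week scan, so 119 and 155 are upper bounds on the patients at risk of being lost.
- **Scan windows.** The scan booking period in 5.3 (12 weeks, with up to two more) lies inside the 10 to 14 week tolerance, so the two do not conflict.

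The defence does not remove the defect. Reading the sentence as a scan definition leads to the missing-central-read default, which also favours non-inferiority. Equal weight on the per-protocol analysis does not help, because the same window applies there. The sensitivity analysis has no stated part in the decision.

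**Conclusion.** The point holds for living patients with progression documented before week 10. The stated inclusion rule conflicts with the intention-to-treat text and the endpoint, and either way of resolving it within the present wording can bias the primary comparison towards non-inferiority.

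The size depends on how many such patients there are, which the documents do not give. With the truth at the margin and exponential progression-free survival, the error is 2.8% to 7.2% against 2.5% if 10% to 50% of pre-week-10 events are dropped, and 3.5% to 15.8% if 5% to 30% of patients with an event by week 12 are scored progression-free. The direction depends on the affected share being similar in the two arms; the size depends on the assumed shares.

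Two stronger readings should not be drawn. The 85% figure is a ceiling that requires every pre-week-10 event to be dropped, including deaths that the protocol counts, and the documents do not make it likely. Late scanning unrelated to arm and outcome does not raise the false-positive rate; it costs power, about 85% to 81.5% at 10% excluded.

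Because the rule governs a primary conclusion and can be corrected in wording, it should be corrected before the analysis.

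**What to change.** In section 12, and in the SAP to match, replace the window sentence for the primary 12-week analysis with these rules:
- All randomised patients stay in the denominator.
- Not progression-free: death, or documented progression (central read or, where none exists, local), at any time from randomisation up to the 12-week assessment, week 14 at the latest.
- Progression-free: alive with no progression at an assessment from week 10 onward, including a later scan that shows none.
- One stated class for patients whose first scan is after week 14 and shows progression, and for those with no scan. For example, class them as not progression-free, with the alternative as a sensitivity analysis.
- Bring the missing-central-read default into line, so that locally documented progression is never scored as progression-free.
- Make the restriction to weeks 10 to 14 the sensitivity analysis.

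Apply the same definitions to the 12-week secondary endpoint of Ir vs IrPan. The cost is a wording change. No new data are needed, because progression, treatment status and deaths are already collected under sections 7.6, 7.7 and 7.9. The sample size does not change.
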